2.4 Study Objectives

2.4.1 Purpose

The purpose of this study will be to prospectively evaluate the outcomes of patients with hepatocellular carcinoma (HCC) who undergo DEB-TACE with the Surefire Precision Infusion System for intentional effect of down-staging patients to OLT.

Patients with HCC and who are being evaluated for liver transplantation but outside Milan criteria and meet the eligibility criteria will be enrolled in the prospective single arm study.

Results of the prospective cohort will be compared to matched historical control patients who were previously treated with DEB-TACE, delivered with standard endhole catheters. This includes all patients treated at the University of Colorado since 2009 treated with 100-300 micron beads for whom follow-up is available.¹ The data are as follows.

	1-Month Response						
	[name] Criteria				Vesselle, G., et al. (2015) Range Criteria		
	0-3 cm	3-7 cm	>7 cm	Total	<5 cm	>=5 cm	Total
Count	84	60	8	152	129	23	152
Range	1.3-3.0 cm	3.2-7.0 cm	7.6-17.0 cm	1.3-17.0 cm	1.3-4.8 cm	5.0-17.0 cm	1.3-17.0 cm
Number Complete Response	33	15	0	48	47	1	48
Percentage Complete Response	39.29%	25.00%	0.00%	31.58%	36.43%	4.35%	31.58%
Number Partial Response	32	39	6	77	58	19	77
Percentage Partial Response	38.10%	65.00%	75.00%	50.66%	44.96%	82.61%	50.66%
Number Stable Disease	14	4	1	19	17	2	19
Percentage Stable Disease	16.67%	6.67%	12.50%	12.50%	13.18%	8.70%	12.50%
Number Progressive Disease	5	1	1	7	6	1	7
Percentage Progressive Disease	5.95%	1.67%	12.50%	4.61%	4.65%	4.35%	4.61%
Number Lost To Follow-up*	0	1	0	1	1	0	1
Percentage Lost To Follow-up*	0.00%	1.67%	0.00%	0.66%	0.78%	0.00%	0.66%
Total	84	60	8	152	129	23	152

¹ We have robust follow-up on these patients, which is the main reason that we are intending to use this historical comparator.

	6-Month Recurrence (Complete & Partial Response)						
	[name] Criteria				Vesselle, G., et al. (2015) Range Criteria		
	0-3 cm	3-7 cm	>7 cm	Total	<5 cm	>=5 cm	Total
Patients with Complete Response at 1-month	33	15	0	48	47	1	48
Number Lost To Follow-up at 6-months	2	3	0	5	5	0	5
Percentage Lost To Follow-up at 6-months	6.06%	20.00%		10.42%	10.64%	0.00%	10.42%
Number No Recurrence at 6-months	19	4	0	23	23	0	23
Percentage No Recurrence at 6-months	57.58%	26.67%		47.92%	48.94%	0.00%	47.92%
Number Recurrent Disease at 6-months	12	8	0	20	19	1	20
Percentage Recurrent Disease at 6-months	36.36%	53.33%		41.67%	40.43%	100.00%	41.67%
Subtotal	33	15	0	48	47	1	48

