Patients with Partial Response at 1-month	32	39	6	77	58	19	77
Number Transplanted	5	3	0	8	7	1	8
Percentage Transplanted	15.63%	7.69%	0.00%	10.39%	12.07%	5.26%	10.39%
Number Continue TACE to Complete Response	4	0	0	4	4	0	4
Percentage Continue TACE to Complete Response	12.50%	0.00%	0.00%	5.19%	6.90%	0.00%	5.19%
Number Continue TACE to Partial Response	6	12	4	22	15	7	22
Percentage Continue TACE to Partial Response	18.75%	30.77%	66.67%	28.57%	25.86%	36.84%	28.57%
Number Continue TACE to Stable Disease	1	5	0	6	2	4	6
Percentage Continue TACE to Stable Disease	3.13%	12.82%	0.00%	7.79%	3.45%	21.05%	7.79%
Number Continue to Progressive Disease	12	10	0	22	21	1	22
Percentage Continue to Progressive Disease	37.50%	25.64%	0.00%	28.57%	36.21%	5.26%	28.57%
Number Continue TACE unknown status	3	3	0	6	5	1	6
Percentage Continue TACE unknown status	9.38%	7.69%	0.00%	7.79%	8.62%	5.26%	7.79%
Number Change Tx	1	4	2	7	2	5	7
Percentage Change Tx	3.13%	10.26%	33.33%	9.09%	3.45%	26.32%	9.09%
Number Deceased by 6-months	0	2	0	2	2	0	2
Percentage Deceased by 6-months	0.00%	5.13%	0.00%	2.60%	3.45%	0.00%	2.60%
Subtotal	32	39	6	77	58	19	77

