3.4 Study Duration

The study was closed by the sponsor on June 18, 2018. All screening, data entry and follow-up visits were ceased on this day. Adverse event follow-ups are still occurring, and are outlined in more detail in Section 4.6.

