For the outcome of tumor response measured as the change in enhancing tumor size (pretreatment – post treatment) we will evaluate changes at 1 month and 6 month separately. We will calculate the difference in tumor enhancement size at 1 month and 6 months using enhancement size at initial treatment as the reference group (i.e. we will have two continuous outcomes which can be positive or negative values). The analyses are exactly parallel for 1 month and 6 month outcomes. We will describe the approach for 6 months. We will fit a general linear model with Kenward-Roger denominator degrees of freedom. The outcome will be the first-differenced 6 month tumor enhancement size. We will use a random intercept to account for correlation between lesions within a given patient. The independent variables will include catheter type, age and sex. We will test the null hypothesis of no association between catheter type and change in tumor enhancement size. In the case that this model fails to converge, or in the case that most patients have only one tumor, we will use an alternative approach. In this alternative approach we will sample one lesion per patient and use ordinary least squares regression and include age and sex as covariates with catheter type as the primary predictor of interest. We will test the null hypothesis of no association between change in tumor enhancement size and catheter type. Should this model also fail to converge, we will simplify further and use a paired t-test comparing initial and 6 month tumor enhancement sizes in a sampled data set (i.e. one tumor per patient), or we will use a Wilcoxon-Mann-Whitney test if the sizes are skewed. We will test the null hypothesis of no association between catheter and tumor enhancement size change.

For the outcome of time to progression, we will quantify the number of weeks from treatment until tumor progression. Failures (or events) will be defined as progression of the tumor per CT examination or AFP level and extrahepatic disease by CT examination, or death due to complications related to the tumor. Censored observations will be defined as patients who we did not observe tumor progression, patients who were lost to follow up, or patients who had a

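### The 6-month size analysis discards lesions that have a 1-month but no 6-month scan; a joint 1- and 6-month model would keep them at little cost

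*Combined protocol and SAP*

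**What the plan says.** Section 2.4.3 makes maximum enhancing diameter at 1 and 6 months the third primary endpoint. Section 4.4 analyses change from baseline: "we will evaluate changes at 1 month and 6 month separately", and "The analyses are exactly parallel for 1 month and 6 month outcomes". For month 6, "The outcome will be the first-differenced 6 month tumor enhancement size". On covariates: "The independent variables will include catheter type, age and sex". On correlation: "We will use a random intercept to account for correlation between lesions within a given patient". Both fallbacks (least squares on one sampled lesion per patient, then a paired t-test or rank test) also need a 6-month size. Section 4.4 gives no missing-data method for this outcome.

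Three places bear on who has a 6-month scan:
- Section 3.4, for the prospective group: "All screening, data entry and follow-up visits were ceased on this day".
- Section 3.11 limits prospective patients with residual disease at 1 month to the 1-month assessment and takes them out of the six-month recurrence evaluation, with an exception for the downstaging population.
- The historical tables in Section 2.4.1 have a row "Number Lost To Follow-up at 6-months" for complete responders. For partial responders they have rows for transplant, unknown status, change of treatment and "Number Deceased by 6-months".

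**The concern.** The random intercept links lesions within a patient, not visits. The 6-month model is therefore a complete-case analysis that ignores a measurement already taken on the same lesion. That always loses some precision. It also biases the catheter comparison if the chance of a 6-month scan depends on 1-month response in a way that differs between groups. There is reason to ask: closure can affect only the Surefire group, Section 3.11 may remove Surefire patients by their 1-month response, and Section 2.4.1 selects controls for having follow-up. A spurious catheter difference, or a masked one, could then appear in a primary endpoint.

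**Working it through.** **The plan's own figures.** The only power calculation (Section 4.3) concerns local recurrence. Its 0.78 for 30% vs 10% is reproduced by a two-sided Fisher test with doubled one-tail p-value (0.780). The documents give no SD, correlation or power for size change, so those inputs below are assumptions.

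**Loss by month 6 in controls (Section 2.4.1).** CR and PR are complete and partial response at 1 month. CR lost: 5/48 = 10.4%. For PR the answer depends on what counts as loss:

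| PR patients counted as lost | n/77 | % | Fisher p vs CR |
|---|---|---|---|
| Unknown status | 6 | 7.8 | 0.75 |
| + 2 deaths | 8 | 10.4 | 1.0 |
| + 8 transplants | 16 | 20.8 | 0.15 |
| + 7 changed treatment | 23 | 29.9 | 0.015 |

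The CR block has no rows for transplant, death or changed treatment. The 19 + 7 = 26 patients with stable or progressive disease have no tabulated 6-month status. None of these rows records whether a scan was done.

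**Bias of the separate model with no true effect.** Assume one lesion per patient, normal 1- and 6-month changes with correlation ρ = 0.5 to 0.8, and SD σ = 1.3 cm. Let CR be the best p = 48/151 = 0.318 of 1-month changes. The cut-point is c = 0.474, with normal density φ(c) = 0.357. If a fraction r of CR and s of non-CR patients are scanned at 6 months, the mean standardised 1-month change of those scanned is

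μ = φ(c)(r − s) / [p·r + (1 − p)·s], and the bias is σρ(μ_Surefire − μ_control).

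Positive values favour Surefire, because change is baseline minus follow-up.

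- *Same response-related loss in both groups:* μ is equal, so the bias is 0. A random 30% closure loss multiplies r and s alike and leaves μ unchanged.
- *Loss unrelated to response:* r = s in each group, so the bias is 0.
- *Controls lose 10% of CR and 30% of all non-CR, Surefire loses at random:* μ_control = 0.357 × 0.2 / (0.318 × 0.9 + 0.682 × 0.7) = 0.0714/0.764 = 0.093 and μ_Surefire = 0. The bias is −1.3 × 0.5 × 0.093 = −0.06 cm to −1.3 × 0.8 × 0.093 = −0.10 cm, or 0.2 to 0.4 standard errors. Simulation gives a similar 0.07 to 0.10 cm.
- *Controls as above, 80% of Surefire non-CR unscanned:* μ_Surefire = 0.357 × 0.7 / (0.318 × 0.9 + 0.682 × 0.2) = 0.250/0.423 = 0.591. The difference is 0.591 − 0.093 = 0.498. The bias is +0.65 × 0.498 = +0.32 cm to +1.04 × 0.498 = +0.52 cm, or 1.0 to 1.6 standard errors.

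**Joint estimate.** In 4,000 simulated trials per setting (100 vs 50), 6-month change was regressed on 1-month change and group, then averaged over all 1-month values. This is the likelihood estimate for two visits when only the second can be missing. It was within about 0.01 cm of zero in every setting above, with variance about 5% to 28% lower. As a rough check, if a fraction f of a group is scanned at random, its variance ratio is 1 − (1 − f)ρ². At f = 0.7 this is 1 − 0.3 × 0.25 = 0.925 to 1 − 0.3 × 0.64 = 0.81.

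**Less idealised data.** A second null simulation (3,000 trials) built sizes from the historical response mix, with SD 1.77 cm and correlation 0.78. Controls were seen at 6 months in 90% of CR and 79% of non-CR:

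| Surefire non-CR seen at 6 months | Separate model (cm) | Type I error | Joint estimate (cm) |
|---|---|---|---|
| 50% | +0.13 | 5.7% | −0.04 |
| 25% | +0.36 | 13% | −0.09 |
| 0% | +0.84 | 36% | −0.20 |

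Random 30% closure alone gave +0.01 cm. At the historical mix 103/151 = 68% are not CR, about 34 of 50 Surefire patients. In the last row, the joint model must extrapolate to all of them, and it over-corrects.

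**Covariance.** With one lesion per patient, two visits identify three quantities: two variances and one covariance. An unstructured two-visit covariance uses all three. A patient random intercept on top would be a fourth parameter and is not identified.

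**The case against.** Separate models per visit are a recognised, prespecified choice, and this is a pilot powered only for local recurrence. That is fair, and it keeps the point to an improvement.

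A reader might infer that the control table shows loss depends on response, from 5/48 against 23/77. It does not. The two blocks list different categories, like for like (lost against unknown) there is no difference, and p = 0.015 requires treating every changed-treatment patient as unscanned. Section 4.5.6 describes standard-of-care imaging every three months, so some of them may have been scanned.

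A reader might also infer a bias of 0.14 to 0.22 cm against Surefire. That needs 60% loss among controls with stable or progressive disease, for whom no 6-month status is given. At 30% it falls to the 0.06 to 0.10 cm above, and at a uniform 10% control loss it is about zero.

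The opposite inference, that Section 3.11 removes every Surefire patient with residual disease and so favours Surefire, is not established either. The rule names recurrence rather than size, and the downstaging exception leaves its reach unclear.

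Two further objections stand and shape the fix. Transplant and death are not plain missing scans. Section 3.11 also counts the 1-month assessment from retreatment, so visits lack a common time origin.

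**Conclusion.** The point holds as a loss of information with a possible bias of unknown size and sign. That lesions without a 6-month scan are dropped follows directly from Section 4.4. That such lesions exist is likely for Surefire and possible for controls, but it is not documented. Under the assumed SD and correlations, the result runs from no bias to about 0.1 cm against Surefire or about 0.5 cm in its favour. The joint estimate's near-zero bias rests on a linear relation between the two visits, on data missing at random given the 1-month size, and on some residual-disease patients being scanned. This is a cheap improvement.

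**What to change.** In Section 4.4, replace the two parallel models with one linear mixed model for 1- and 6-month change:

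- Fixed effects: catheter, visit, catheter-by-visit, and age and sex each by visit. Use Kenward-Roger degrees of freedom and read both catheter contrasts from this model.
- Data: every lesion with at least one post-treatment scan.
- Covariance: unstructured for the two visits. Add a patient random intercept only if enough patients have several lesions. In the one-lesion fallback, use the unstructured two-visit model without it.
- Keep the present separate models as the last fallback and as a sensitivity analysis.
- State that scans missing through loss to follow-up or study closure are treated as missing at random. State separately how transplant, death and change of treatment are handled.
- Record time from first treatment where the 1-month scan is counted from retreatment.
- Report, by group and 1-month response, how many lesions have a 6-month size.

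The cost is SAP wording on data already collected, extra covariance parameters and open reliance on a missing-at-random assumption. The model does not repair Section 3.11. The plan should say whether that rule reaches the size endpoint. If no residual-disease Surefire patient has a 6-month scan, the 6-month contrast should be labelled as extrapolation.

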1. STUDY OVERVIEW

1.1 Study Flowchart

1.2 Study Summary

Title	Bridge to Orthotopic Liver Transplantation (OLT) - (Surefire Precision vs Endhole Embolization with DEBTACE)
Short Title	SPEED 1
Protocol Number	16-1313
Phase	Phase IV – Post Market
Methodology	Single Arm Prospective
Study Duration	2 years
Study Center(s)	University of Colorado Hospital
Objectives	Prospectively evaluate the outcomes of patients with hepatocellular carcinoma (HCC) who undergo DEB-TACE with the Surefire Precision Infusion System for intentional effect of down-staging patients to OLT.
Primary Endpoints	
• Tumor Response (mRECIST criteria) at 1 month• Local recurrence rate (LRR) at 6 months
Number of Subjects	50
Diagnosis and Main Inclusion Criteria	Patients with HCC and who are being evaluated for liver transplantation but outside Milan criteria and have been prescribed DEB-TACE for tumor down-staging.
Study Product(s), Dose, Route, Regimen	DEB-TACE delivered with the Surefire Precision Infusion System

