2.1.4 High Recurrence Rates after standard TACE

The likelihood to achieve any response following TACE significantly depends on treatment, tumor number [66] and tumor size with radiologic Complete Response (CR) rates of up to 77% in tumors <2 cm in size but only 25% in tumors with diameters of >5 cm after the first TACE [68]. Similar size dependent differences in radiologic response also apply to repeated TACE sessions. While retreatment with multiple treatments shows a CR rate of 55% and 40% respectively in lesions <5 cm, CR rates are 25% and 0% in a tumor >5 cm. (12)

Furthermore, once complete radiologic response is achieved, overall 72% will suffer tumor recurrence after a median of 8.5 months of which 31% will present as local, 40% as distant intrahepatic and 27% a mixed (local and distant intrahepatic) relapse of disease and again, tumors >5 cm showed a significantly shorter time to recurrence (6 months, $p < 0.05$) (12)

Thus, typical patients requiring downstage have tumors > 5cm but have the poorest response rates requiring multiple procedures and hampered by a high recurrence rates.

2.1.5 Current Delivery Techniques with Standard Endhole catheters.

Currently the best results for TACE occur when the dose is delivered in a highly targeted manner into the tumor. Dense accumulation of embolic spheres or lipiodol into the tumor as documented by CT has been shown to have improved outcomes (13, 14). However, with standard endhole catheters achieving maximum delivery of embolic agents is limited by the development of stasis, non-target delivery and subsequently non target injury. Thus, often Interventional Radiologist use a crude angiographic endpoint of stasis or substasis as the current endpoint.

As DEB-TACE is performed through an endhole catheter with either stasis or substasis as an endpoint, this current methodology is extremely subjective, lacks a quantifiable endpoint and results in various degrees of embolization on patients. Thus, a significant variability on the delivery techniques and endpoints.

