2.4.3 Primary Endpoints

1. Tumor response (modified RECIST criteria) at 1 month as shown by contrast enhanced CT/MRI. (Note: Tumor response will be determined on a per-treated lesion basis.)
2. Local recurrence rate (LRR) at 6 months as shown by contrast enhanced CT/MRI
3. Absolute Tumor enhancing maximum diameter at 1M and 6M.

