4.4 Statistical Analysis Plan

All statistical tests use a type I error rate of 0.05. We will calculate descriptive statistics for all variables of interest including means, medians and standard deviations for continuous measures, and frequencies and percents for categorical variables. These calculations will be performed overall and stratified by treatment assignment. We will compare baseline characteristics between the treatment and retrospective groups. We will test for differences using independent samples t-tests (alternatively, Wilcoxon-Mann-Whitney tests if data are skewed) for continuous variables, and Chi-square tests (alternatively Fisher's exact tests if some cells are sparse) for categorical variables.

For the outcome of local recurrence rate (LRR) we will test the null hypothesis of no difference in the proportion of patients with local recurrence by catheter type using a Fisher's exact test.

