liver transplant before evidence of progression was found. For censored observations the time at risk will be calculated as the time from treatment initiation to the last known clinical encounter (for no progression or lost to follow up), or to liver transplant (for patients who had a liver transplant before evidence of progression was found); this will be measured in weeks. To test for differences in time to tumor progression between the treatment and the retrospective group, we will use Cox proportional hazards regression. Treatment group will be our primary predictor of interest, and we will include age, sex and a variable approximating stage/severity at time of treatment using homogenous groups. We will test the null hypothesis of no association between time to progression and treatment group.

For the outcome of survival time, we will quantify the number of weeks from treatment until death. Failures (or events) will be defined as death related to the tumor. Censored observations will be defined as patients who we did not die during the follow up period, or patients who were lost to follow up. For censored observations the time at risk will be calculated as the time from treatment initiation to the last known clinical encounter; this will be measured in weeks. To test for differences in survival time between the treatment and the control group, we will use Cox proportional hazards regression. Treatment group will be our primary predictor of interest, and we will include age, sex and a variable approximating stage/severity at time of treatment using homogenous groups. We will test the null hypothesis of no association between survival time and treatment group.

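### The change-in-enhancing-size models compare non-randomised groups on absolute change without adjusting for baseline tumour size, so any size imbalance would be read as a catheter effect

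*Combined protocol and SAP*

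**What the plan says.** Section 4.4 defines the outcome as a pretreatment minus post-treatment difference: "The outcome will be the first-differenced 6 month tumor enhancement size", with a parallel analysis at 1 month. The main analysis is a model with a random intercept per patient: "The independent variables will include catheter type, age and sex". If it fails to converge, or most patients have one tumour, one lesion per patient is sampled and ordinary least squares is used, to "include age and sex as covariates with catheter type as the primary predictor of interest". Neither model has a term for size, stage or severity. Both Cox models in the same section do: "a variable approximating stage/severity at time of treatment using homogenous groups".

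On comparability, Section 4.4 says "We will compare baseline characteristics between the treatment and retrospective groups", but attaches no adjustment to the result. Sections 2.4.1, 2.4.2 and 3.1 (with footnote 2) call the controls matched and name no matching variable. Section 3.3 says they are randomly sampled.

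Section 2.4.3 lists "Absolute Tumor enhancing maximum diameter at 1M and 6M" as a primary endpoint. Section 1.2 does not; it lists "Tumor Response (mRECIST criteria) at 1 month" and local recurrence at 6 months.

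**The concern.** The outcome is in absolute units (Section 4.4 gives none; centimetres are taken from the tables in Section 2.4.1). A complete response scores the whole baseline diameter, so the outcome depends on starting size even when both catheters work equally well. In a randomised trial the groups would balance on size on average. Here they need not, and age and sex do not stand in for size. The random intercept handles correlation between lesions within a patient, not a size difference between groups.

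An imbalance is easy to imagine. In the control pool 23 of 152 (15%) are 5 cm or more, while Section 2.1.4 says that "typical patients requiring downstage have tumors > 5cm". Simple random sampling would carry the pool's size mix into the control group. At stake is whether a significant catheter term can be told apart from a difference in tumour size.

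**Working it through.** **The plan's own figures.** The plan gives no sample size or power for this outcome. Section 4.3 concerns local recurrence only. Its power of 0.78 (30% vs 10%, 100 vs 50) reproduces as 0.778 with a continuity-corrected arcsine approximation, but does not bear on this point.

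**Inputs from the documents.** Crossing the two size groupings of the 1-month table in Section 2.4.1 gives four cells (for example, 3.2-4.8 cm complete responses = 47 - 33 = 14).

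**Assumptions.** There is no catheter effect, and both groups have the same size-specific response rates. Enhancing diameter before treatment equals tabulated size, taken at cell midpoints. Fractional shrinkage is 1 for complete response (CR), 0.30 to 0.99 for partial response (PR, mean 0.645), -0.20 to 0.30 for stable disease (SD, mean 0.05) and -0.60 to -0.20 for progression (PD, mean -0.40). Section 4.5.1 fixes only the category limits.

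**Step 1: mean loss per cell** = (CR x 1 + PR x 0.645 + SD x 0.05 - PD x 0.40) / evaluable x mid-diameter.

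| Size, cm | n | CR/PR/SD/PD | Mean fraction | Midpoint, cm | Loss, cm |
|---|---|---|---|---|---|
| 1.3-3.0 | 84 | 33/32/14/5 | 0.623 | 2.15 | 1.34 |
| 3.2-4.8 | 45 (1 lost) | 14/26/3/1 | 0.694 | 4.0 | 2.77 |
| 5.0-7.0 | 15 | 1/13/1/0 | 0.629 | 6.0 | 3.77 |
| 7.6-17.0 | 8 | 0/6/1/1 | 0.440 | 12.3 | 5.41 |

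**Step 2: contrast.** Below 5 cm: (84 x 1.34 + 45 x 2.77)/129 = 1.84 cm. At 5 cm or more: (15 x 3.77 + 8 x 5.41)/23 = 4.34 cm. Difference: 2.50 cm.

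**Step 3: bias** = contrast x (Surefire share at 5 cm or more - 0.151). With 2.50 this gives 0.25, 0.50 and 0.87 cm at shares of 25, 35 and 50%, and -0.25 cm at 5%.

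**Step 4: vary depth of partial response.** If mean depth in tumours of 5 cm or more is 50, 40 or 30%, with 64.5% kept for smaller tumours, the contrast falls to 1.55, 0.89 or 0.23 cm. If every partial response in both size groups sits at the 30% floor, it is 0.70 cm, and the bias is 0.07, 0.14 and 0.24 cm.

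**Step 5: simulate the least squares fallback.** 50 vs 100, control sizes as tabulated, age and sex unrelated to outcome, nominal 5%. Ranges in the first two rows are across repeated runs; in the third, across the 8 cm cap and 5-7 cm only.

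| Scenario | Bias, cm, at 25/35/50% | Rejection, % |
|---|---|---|
| Surefire sizes as control table | 0.25-0.26 / 0.49-0.51 / 0.87-0.88 | 12 / 26-28 / 54-56 |
| Same, large-tumour PR 0.30-0.60 | 0.12-0.14 / 0.22-0.24 / 0.43 | 7-8 / 12-13 / 30 |
| Surefire capped at 8 cm, or large ones all 5-7 cm (PR 0.30-0.99) | 0.07-0.10 / 0.25-0.28 / 0.54-0.59 | 5-6 / 12-13 / 33-41 |

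With equal mixes there is no bias and rejection is 5%. With 5% large, there is a spurious harm of 0.26-0.28 cm and 9-11% rejection. With 20 or 30 Surefire patients the bias is unchanged and rejection over the first and capped scenarios is 4-38% or 5-44%. A mixed model with an assumed 1 to 3 lesions per patient (within-patient correlation 0.5, between-patient degrees of freedom in place of Kenward-Roger) gives essentially the same bias.

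**Step 6: add baseline diameter (50 vs 100, PR 0.30-0.99).** Residual bias is 0.00-0.13 cm at 25-35% and 0.02-0.19 cm at 50%. Rejection is 5-7% and 7-13% with ordinary standard errors, and 4-8% with HC3. Percent change with the same diameter term rejects in 2-6% of runs.

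**The case against.** The strongest reply is on size. The 2.50 cm contrast gives large and small tumours the same depth of partial response, which the documents do not report. They hint otherwise: Section 2.1.4 describes the poorest response in large tumours, and complete response falls from 39% at 0-3 cm to 0% above 7 cm in Section 2.4.1. This stands. Step 4 shows how far the contrast can fall, so the first row of step 5 is an upper-end illustration for mixes with larger Surefire tumours. The midpoint of 12.3 cm for only eight tumours also pushes it up.

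Second, no imbalance is shown. Sections 1.2 and 2.4.1 describe patients outside Milan, but inclusion criterion 3 also admits patients within Milan, and outside Milan need not mean large: four 2 cm lesions fail Section 4.5.3. This stands too. A reader might infer that Surefire tumours are larger and that the analysis therefore favours the device; the documents support neither step.

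Third, matching is stated, so it would be too strong to say that covariates are the only protection. But with no variable named, and random sampling in Section 3.3, it does not ensure balance on size.

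Fourth, the response rates are 1-month rates. A reader might carry the figures over to 6 months; nothing here supports that. Section 3.11 limits who is evaluated for 6-month recurrence, so the 6-month set may also be selected on response.

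Finally, this is a closed pilot sized on local recurrence, and its stated hypothesis (Section 2.4.2) is mRECIST response. That limits the weight of the point but does not remove the flaw from an outcome that Section 2.4.3 calls primary.

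**Conclusion.** The point holds in conditional form. Both models for change in enhancing size leave out baseline size, and nothing in the plan ensures that the groups balance on it. If sizes differ, the catheter term absorbs the difference, in either direction; if they do not, there is no bias.

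For 1 month, a spurious benefit of up to about 0.25, 0.5 and 0.9 cm, with false rejection up to about 12, 27 and 55%, corresponds to 25, 35 and 50% of Surefire tumours at 5 cm or more. With shallower partial responses in large tumours it is about 0.14, 0.22 and 0.43 cm, with 8, 12 and 30%. It is lower again at the 30% floor and, in the 25% case, if large Surefire tumours cluster at 5-8 cm. These figures rest on assumed Surefire sizes and assumed depth of partial response.

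The 6-month model has the same flaw, but its magnitude was not computed. It would be wrong to extend the point to the mRECIST hypothesis: that response is classified on proportional change, so this scale problem does not reach it. The change is a free improvement, made without waiting to learn whether sizes differ.

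**What to change.** In Section 4.4:

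- Add baseline enhancing maximum diameter to catheter type, age and sex, in the mixed model and in the least squares fallback, at 1 and 6 months.
- Use HC3 standard errors in the fallback, because residual spread grows with tumour size.
- Report the baseline size distribution of each group beside the estimate.
- Add percent change from baseline, with the same covariates, as a sensitivity analysis. A log ratio would need a further rule, because a complete response leaves zero enhancing diameter (48 of 152 controls, 32%).
- State that a linear size term removes most but not all of the bias, and that it does not correct selection on response into the 6-month set.

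The cost is SAP wording and one degree of freedom per model. Baseline enhancing size is already needed to compute the change, so the June 2018 closure of data entry (Section 3.4) is no obstacle. The conflicts over matched versus randomly sampled controls, and over whether this outcome is primary, also need reconciling, but this fix does not depend on them.
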